14.3 Balancing the benefits and harms of the study

The intervention: Patient decision aid (PtDA)

There are no obvious harms from using a PtDA. A Cochrane systematic review and metaanalysis evaluating 50 different PtDAs from 105 studies, provides evidence that PtDAs are more likely to benefit patients, compared to usual care¹³. Patients receiving a PtDA are more likely to have accurate risk perception and select a treatment that is more congruent with their values and preferences. The review found no negative effect on health outcomes between the PtDA and usual care groups, indeed, some studies found a reduction in symptoms of anxiety.

In non-emergency situations, it is an ethical and legal requirement that patients provide informed consent before medical treatment. Patients must therefore be fully informed about their options. The PtDA provides comprehensive information about their treatment options (coronary angioplasty or medical therapy) including the potential risks, benefits, and side-effects. It is possible that patients may change their mind about having elective coronary angioplasty after receiving the PtDA. However, this is no different to usual care; patients in the control group who receive usual care (i.e., patient information leaflet) are also free to change their mind about having the procedure. We will record the number of patients in both groups who choose to receive medical therapy only, following referral for elective angioplasty. Receiving the PtDA will not replace consultations with the cardiologist or cardiac specialist nurse.

Participating in the interview

In the unlikely event that a participant becomes distressed during the research interview, the interview will be stopped. The participant will be given the option to terminate the interview or reconvene when they feel ready. The British Heart Foundation has a free patient line, which provides support and counselling. Details of this resource will be made available to participants and included in the participant information sheet. Participants will be able to stop the interview or withdraw from the study at any time without giving a reason. The Research Fellow will be conducting interviews alone remotely via telephone or Microsoft Teams. They can choose to end the interview if the participant displays inappropriate behaviour or makes inappropriate and personal remarks. Regular debriefs between Research Fellow and supervisory team will be scheduled.

Data protection and patient confidentiality

Participants will be reassured that confidentiality will be maintained unless information is disclosed during the interview, which raises concerns about their safety or poor clinical practice. Information about confidentiality and data storage will be included in the participant information sheet and consent form.

Data will be stored in accordance with the General Data Protection Regulation (GDPR) 2018 and the Data Protection Act 2018. Following informed consent, participants will be assigned a unique study identification number. To support anonymity, study documents relating to each participant will contain only the participant ID number and no personal data (i.e. name, address, DOB). However medical and demographic data will be included. A password protected linkage log (recording hospital number and unique participant study number), stored by each participating NHS Trust as per their data protection policy, will allow re-identification of patient participant data if required). The interview transcripts will be anonymised by removing all identifies (e.g., names, locations). All participants involved in the research will be anonymised in any publications or reports. Once participation is completed, all personal data that has been retained to communicate with the participant will be kept for one year in case further correspondence is required. Anonymised research data generated from the study will be retained and stored in the study Sponsor's Storage server for up to 10 years in line with the University Data Protection Policy and the Medical Research Council (2017) Retention Framework for Research Data and Records. Henceforth, the study co-Sponsor (Open University) will be responsible for data security.

Financial and other competing interests for the chief investigator, PIs at each site and committee members for the overall study management

The Chief Investigator, co-lead, and several co-investigators were involved in the development of CONNECT. Having conducted a market analysis it was concluded that CONNECT would be unlikely to have any commercial value but may be of interest to industry partners who may want to take over the ownership and embed CONNECT as part of their offer to their customer base. CHFT will own the foreground IP. So, there are potential ownership interests to disclose that could be potentially affected by the study results. We will/ convene a steering group with representation to discuss plans regarding the use of CONNECT after study completion. At the time of writing the protocol not all sites/personnel may have been identified. When this is the case then the protocol should state that this information will be collected and where it will be documented.

14.4 Adverse Events

We discussed the possibility of adverse events with consultant cardiologists and their expert opinion was that there were no obvious adverse events associated with using CONNECT which is an educational resource with built in interactive learning aimed to encourage patient involvement in the shared decision-making process. A Cochrane review on PtDA reported no adverse events because of using PtDAs¹³. However, we will record MACE, defined as acute myocardial infarction, death due to a cardiac or unknown cause, emergency revascularization, ventricular arrhythmia, or cardiogenic shock) and rates of hospital readmission 30-days after hospital discharge.

14.5 Participant Incentives

Patient participants completing the main feasibility study will be entered into a prize draw for a gift voucher in acknowledgement of their time (one prize draw per site). Patient participants taking part in the interview will also receive a gift voucher.

14.6 Research Ethics Committee (REC) and other Regulatory review & reports

Before the start of the study, a favourable opinion will be sought from the UK NHS Research Ethics Committee (REC) and Health Research Authority (HRA). Amendments to the protocol or associated documents (i.e., consent form, participant information documents) will firstly be sent to the study sponsor for approval prior to submission to the NHS REC and HRA for approval. The participating sites' R&D department and local PI will also be notified to any pending amendment. All approved study documents will have a version number and date. Current versions of study documents and amendments will be tracked in a log which will be updated by a member of the study management group. The research plan has been independently reviewed by external expert reviewers, not directly involved in the study, as part of the National Institute for Health research review process. The Investigator should not deviate from the protocol. Any deviations from the protocol will be documented in a protocol deviation form and reported to the Chief Investigator and Sponsor immediately.

15. DISSEMINATION POLICY

We will disseminate the study's findings to patients and the public via a national one-day dissemination event/conference 'Using Patient Decision Aids to Support Shared Decision Making in Cardiology'. The event will be advertised to patients and members of the public through established networks such as the Cardiovascular Care Partnership, Heartbeat: The Brighouse Heart Support Group, and CREW Heart Support Group. We will share study findings with Heart Research UK, the British Heart Foundation, and their patient British Heart Foundation support

groups. Study participants will also be invited to the event. We will also write a 'Plain English' report of the study findings with input from the PPI Group. The report will be disseminated to the networks mentioned above, including the European Society of Cardiology and British Cardiac Society, which both have patient advocacy groups.

The Chief Investigator will draft the final report and associated outputs with input from all members of the research team. All research team members will be authors providing their contribution aligns with guidance on defined authorship criteria ethical publication Committee on Publication Ethics. There will be no professional writers used.

17. APPENDICES

Appendix 1: Description of CONNECT

CONNECT is described below using the Template for Intervention Description and Replication (TIDieR) checklist, which aims to improve the completeness of reporting of interventions.

NAME: CONNECT is a Patient Decision Aid (PtDA), which is a complex intervention (It is not a medical device). CONNECT is accessible at the following link https://uoh-connect.staging.ginger-root.co.uk/. Preliminary testing with 63 patients/health professionals indicates that CONNECT shows promise, but it has not yet been tested in NHS settings. Preliminary acceptability findings were presented at the Health Services Research UK 2020 annual conference. The presentation can be viewed at the following link: https://www.youtube.com/watch?v=9pvWG0-EF2U.

WHY: Research shows that patients diagnosed with stable angina, who are making decisions about an invasive procedure (coronary angioplasty) have unmet decision support needs. CONNECT was developed in response to this unmet need, using International Patients Decision Making Standards, which are underpinned by decision theory. PtDAs are effective tools to improve the quality of shared decision making (SDM).

WHAT: Like other PtDAs, CONNECT is a 'tool' designed to help people to take part in decision-making about treatment options. It uses multimedia (images, diagrams, animations, audio) to make patients aware of their treatment choices, associated risks and benefits and includes interactive activities (i.e., questions about angina symptoms, what matters to them and treatment choice) to clarify and communicate patients' personal values that are associated with different aspects of each treatment option. CONNECT provides a personalised summary (see section 2 for example), which can be saved as a PDF file and gives details of patients' angina symptoms, the impact of these on daily life, personal values, treatment preferences, worries, concerns, and any unanswered questions. This personalised summary can inform patient consultations and potentially act as a 'primer' for health professionals, alerting them to specific areas that the patient may wish to discuss.

HOW: CONNECT is a web based PtDA that supports individual self-directed learning at a pace set by the user. It was co-created with patients and health professionals and can be used on multiple devices (computer, iPad, tablet, or mobile phone).

WHO: Health Professionals (Cardiologists and Specialist Cardiac Nurses) implementing CONNECT will receive training on SDM and using CONNECT.

WHEN/WHERE/HOW MUCH: Patients on the waiting list for planned coronary angioplasty will receive a link to CONNECT along with instructions, which they can use at home ahead of a (usual care) pre-assessment consultation (30-45 minutes) with a specialist cardiac nurse. Following discussions, we know that there are variations in how NHS Trusts contact patients (paper letter, text message, QR code, patient portals) to communicate upcoming consultations and share

patient information. Therefore, the link to the CONNECT website will be delivered flexibly according to the Trust's preferences. The instructions for accessing and using CONNECT will include frequently asked questions, which will be informed from our preliminary acceptability findings. The time taken to use CONNECT varies according to the user. Estimates from our study in non-clinical settings showed that patients took up to an hour to work through the content and appreciated being able to revisit CONNECT multiple times if needed.

## 1. Introduction

This statistical analysis plan (SAP) is written in conjunction with the International Conference on Harmonisation topic E9 [1] and trial documents (Protocol, case report form (CRF) and Data Validation Specifications). The SAP will guide the statistician during the statistical analysis of all quantitative outcomes in order to answer the objectives of the study.

#### 1.1. Background and rationale

Patient Decision Aids (PtDAs) are evidence-based interventions known to be effective in improving the quality of shared decision-making.

The CONNECT feasibility study is a cluster randomised controlled feasibility study with an embedded qualitative study. Eight clusters (NHS Trusts providing planned coronary angioplasty in England) will be recruited and randomised to the control or intervention arm at a 1:3 allocation ratio. Six clusters will implement a digital Patient Decision Aid 'CONNECT' and two clusters will provide usual care only. Questionnaires will be administered before and after delivery of intervention or control.

The overarching aim of this study is to determine whether it is feasible to conduct a cluster Randomised Controlled Trial (c-RCT) to test the effectiveness of CONNECT for improving shared decision-making for patients with stable angina.

The quantitative and qualitative data collected will enable us to assess:

- 1) the feasibility of delivering CONNECT in the planned coronary angioplasty patient pathway;
- 2) explore the acceptability of CONNECT to patients and cardiology teams;
- 3) assess the feasibility and acceptability of trial procedures.

#### 1.2. Objectives

The primary objective of this study is to determine the feasibility of proceeding to a definitive trial. We will achieve this aim by the completion of the following objectives:

- 1) Determine the feasibility of recruitment and retention.
- 2) Evaluate willingness to be randomised.
- 3) Determine diversity and inclusivity of sample.
- 4) Explore the characteristics and appropriateness of questionnaires as outcome measures for c-RCT.
- 5) Estimate the Intra-cluster Correlation Coefficient and sample size calculation for a c-RCT.
- 6) Explore the practical implementation of CONNECT.
- 7) Evaluate the acceptability of CONNECT and study procedures.

## 2. Study Methods

#### 2.1. Trial design

This is a two group, unblinded, multi centre, parallel cluster randomised controlled feasibility study with an embedded qualitative study. Clusters will be NHS Trusts that provide planned coronary angioplasty treatment for adults. Eight clusters will be recruited and randomised to the control or intervention arm at a 1:3 allocation ratio. Participants (n=320; 40 per cluster) will be patients with stable angina who are on the waiting list for planned coronary angioplasty or planned diagnostic coronary angiography with the potential to proceed immediately to treatment with coronary angioplasty ("angio query proceed"). Participants recruited from clusters in the intervention arm will receive the digital PtDA 'CONNECT'. Participants recruited from clusters in the control arm will

receive usual care. Questionnaires will be administered before and after delivery of intervention or control.

#### 2.2. Randomisation

The eight Cardiology Departments are the units of analysis and will be randomised using stratified block randomisation with an allocation ratio of 3:1 to the intervention group and block size of four. Cardiology Departments will be stratified as appropriate, by factors such as the presence, or absence, of on-site surgical provision.

There will be no blinding, as the intervention will be delivered by the research nurse and cardiology teams. Randomisation will be conducted by the study statistician [name] and the statistician will conduct the randomisation blinded.

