3. STUDY DESIGN AND SETTING

3.1 Study design

This is a cluster randomised controlled feasibility study with a nested qualitative study. Figure 1. shows the flow chart for this multi-centre, unblinded, two group, prospective, cluster randomised, controlled feasibility study. Our statistician advised that a minimum of eight clusters in total is needed to best estimate the Intra-cluster Correlation Coefficient (ICC)¹⁷. We aim to recruit eight clusters (NHS Cardiology Departments delivering care for patients scheduled to have planned coronary angiogram query proceed or planned coronary angioplasty in England) which will be

randomised to the control or intervention arm at a 1:3 allocation ratio. Six clusters will implement a digital Patient Decision Aid 'CONNECT' and two will be usual care.

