4.3 Patient Participants (Nested Qualitative Study)

From the 240 patient participants recruited to the intervention arm of the main feasibility study, we will recruit a sub-sample of up to 40 patient participants (6-7 from each Cardiology Centre). Eligible patients will be those who are participating in the feasibility study and have not withdrawn from the study.

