6.2. Randomisation

The eight Cardiology Departments are the units of analysis and will be randomised using stratified block randomisation with an allocation ratio of 3:1 to the intervention group and block size of four. Cardiology Departments will be stratified as appropriate, by factors such as the presence, or absence, of on-site surgical provision.

Details of the Cardiology Departments in England that have expressed an interest in participating in the study through the submission of an Expression of Interest document will be recorded. A separate linkage file will be developed by the Chief Investigator or delegate (Co-Lead, Research Fellow) in which each Cardiology Departments will be anonymised through the allocation of a unique identifier. In this way the identity of participating Cardiology Departments will be blinded to the study statistician, who will generate the allocation sequence (computer generated random numbers) and implement it.

The allocation ratio was chosen to maximise the number of clusters in the intervention arm to test the feasibility, practicality, and acceptability of the intervention. A control arm was included to evaluate the feasibility and acceptability of trial procedures such as the willingness of Cardiac Departments to be randomised. This study is not a 'mini-version' of the future c-RCT designed to test the effectiveness of the intervention.

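### Stratified blocks of four at 3:1 do not guarantee the stated six intervention and two control sites; an uneven split on on-site surgery can leave a single control site

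*SAP*

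**What the plan says.** The split of sites is stated as a fixed result. SAP 1.1 reads: "Six clusters will implement a digital Patient Decision Aid 'CONNECT' and two clusters will provide usual care only". Protocol 3.1 says the same: "Six clusters will implement a digital Patient Decision Aid 'CONNECT' and two will be usual care". Protocol 4.3 carries the split into patient numbers: "From the 240 patient participants recruited to the intervention arm of the main feasibility study".

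The method is given in SAP 2.2 and in matching words in Protocol 6.2: the departments are to be "randomised using stratified block randomisation with an allocation ratio of 3:1 to the intervention group and block size of four". On the strata, both documents say only this: "Cardiology Departments will be stratified as appropriate, by factors such as the presence, or absence, of on-site surgical provision".

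Neither document fixes the number of factors or strata, gives the number of sites per stratum, says what happens to a part-filled block, or holds the total at 6:2. Protocol 3.5 treats eight sites as a maximum. The amber band for cluster recruitment is 6-7 sites in Protocol Table 1 and 5-7 in the revised criteria of SAP 4.1.1.

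**The concern.** A block of four at 3:1 holds exactly one control slot. Blocks deliver the intended ratio only when they are filled, and eight sites fill just two. Once the eight are divided into strata, blocks can be left part-filled, and whether the control slot falls in the used part is then a matter of chance. The stated method can therefore fail to deliver the stated design.

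At stake is mainly the between-arm comparison. SAP 4.1 estimates the difference in Decisional Conflict Scale score with hospital as a random effect. It uses the interval to judge whether the likely effect is clinically relevant and to inform the definitive sample size. With one control site, the contrast between arms is also a contrast between that site and the rest. The model can still be fitted, but only by assuming that the variation seen among intervention sites also applies to usual care, which one control site cannot show.

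**Working it through.** **Inputs.** Eight sites at 3:1 (SAP 2.1 and 2.2); blocks of four with three intervention slots and one control slot (SAP 2.2, Protocol 6.2); 40 patients per site (SAP 2.1). The documents give no stratum sizes, so every split of eight sites on one binary factor is examined.

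**Step 1, the plan's own figure.** 8 × 3/4 = 6 intervention sites and 8 × 1/4 = 2 control sites; 6 × 40 = 240 intervention patients. The stated split is reproduced as the expected result. It is also the certain result if there is no stratification.

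**Step 2, the rule.** Write a stratum of s sites as s = 4q + r, with r from 0 to 3. The q full blocks give q controls for certain. The part-filled block gives one more with probability r/4. Strata are independent.

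**Step 3, one binary factor, eight sites.**

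| Split | Remainders r | P(1 control) | P(2 controls) | P(3 controls) |
|---|---|---|---|---|
| 8/0 or 4/4 | 0, 0 | 0 | 100% | 0 |
| 5/3 | 1, 3 | 18.75% | 62.5% | 18.75% |
| 7/1 | 3, 1 | 18.75% | 62.5% | 18.75% |
| 6/2 | 2, 2 | 25% | 50% | 25% |

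For 5/3, one control is certain from the full block. Then P(1) = (1 − 1/4)(1 − 3/4) = 3/16, P(3) = (1/4)(3/4) = 3/16, and P(2) = 10/16. The 7/1 split has the same remainders. For 6/2, P(1) = (1/2)(1/2) = 1/4, and P(3) is the same.

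As an assumption, since the documents give no prevalence, let each site independently have the factor with probability between 20% and 50%. Averaged over splits, P(1) is about 15-17%, P(3) equals P(1), and P(2) is about 66-70%.

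**Step 4, no control site.** A stratum of four or more sites contains a full block and so a control. Zero controls therefore requires every stratum to hold fewer than four sites. Two such strata hold at most 3 + 3 = 6 sites, so with eight sites and one binary factor it cannot happen. It needs at least three strata. For 2/2/2/2 the probability is (1/2)^4 = 6.25%. With fewer than eight sites, one binary factor is enough: six sites split 3/3 give (1/4)(1/4) = 6.25%, and five split 3/2 give (1/4)(1/2) = 12.5%.

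**Step 5, effect on the arm difference.** With equal site sizes and the same variance of site means in both arms, the variance of the difference is proportional to 1/(intervention sites) + 1/(control sites).

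- 6:2 gives 1/6 + 1/2 = 0.667.
- 7:1 gives 1/7 + 1 = 1.143; SE ratio to 6:2 is √(1.143/0.667) = 1.31.
- 5:3 gives 1/5 + 1/3 = 0.533; SE ratio to 6:2 is √(0.533/0.667) = 0.89.

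In patients, 7:1 means 280 and 40 (7 × 40, 1 × 40), and 5:3 means 200 and 120 (5 × 40, 3 × 40), against the planned 240 and 80.

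**The case against.** The strongest reply is that the text leaves stratification to judgement. If the statistician uses no factor, or the sites divide 4/4, blocks of four give exactly 6:2. That stands, and 6:2 is the most likely single result under every split of eight sites on one binary factor. The text permits a sound scheme, but it does not require one, and it names a factor whose split across the recruited sites is not stated.

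Second, half of the 37.5-50% chance of missing 6:2 is three controls, which improves the precision of the arm difference. That also stands. The harmful part is the 18.75-25% chance of one control. Three controls mainly upset the stated counts and the interview plan built on six intervention sites (Protocol 6.1.3).

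Third, this is an unpowered feasibility study. Protocol 6.2 includes the control arm to test trial procedures, most progression criteria use total sites or the whole patient sample, adherence comes from the intervention arm alone, and the ICC is justified by eight clusters in total (SAP 2.3.1). All of this is correct. A reader might infer that the whole plan depends on exactly two controls; it does not. What depends on the number is the SAP 4.1 arm difference and the summaries by group. Even two control sites say little about variation in usual care.

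**Conclusion.** The point holds as a mismatch between the stated method and the stated result. From eight sites, stratified blocks of four guarantee 6:2 only for stratum sizes that are multiples of four. For an uneven split on on-site surgery, the chance of a single control site is 18.75% (5/3 or 7/1) or 25% (6/2). In that case the arm difference is confounded with one site and its standard error is about 31% larger than planned. These figures are conditional on the split, which the documents do not give; the 31% also assumes equal site sizes and equal variance of site means in the two arms.

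Two stronger readings are tempting. One is that 6:2 can arise only with multiples of four; in fact it still arises 50-62.5% of the time for the uneven splits above. The other is that the study may finish with no control arm. With eight sites that needs at least three strata, hence factors the documents never name. Even with two independent factors at assumed prevalences of 30-50%, the chance averages about 1-2%. It becomes possible with the single named factor only if fewer than eight sites are randomised.

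**What to change.** Replace the stratified blocks in SAP 2.2 and Protocol 6.2 with a draw that holds the total at six and two. Either of these does so:

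- Once all eight anonymised sites are known, draw one of the 8 × 7 / 2 = 28 possible 6:2 allocations at random.
- If sites must open earlier, use two unstratified blocks of four.

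If balance on on-site surgery is wanted, name it as the only factor and restrict the draw to allocations with one control in each stratum, where both strata hold at least two sites. With unequal strata, a site's chance of being control then differs: 1/5 against 1/3 for a 5/3 split, 1/6 against 1/2 for 6/2. The SAP should say so and account for on-site surgery in the analysis; it is not among the SAP 4.1 covariates now.

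State in advance the number of control sites, at least two, if fewer than eight sites are recruited. Unstratified blocks alone do not settle this: with seven, six or five sites, the part-filled second block leaves one control with probability 25%, 50% or 75%.

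The cost is a few lines of R and a wording change in both documents. Sites wait until their batch is complete to learn their allocation, and stratification is lost or limited. Randomisation cannot be repaired afterwards, so the text should be settled before allocation. If allocation has already been done, report the factors used, the stratum sizes and the split obtained.
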